## **4.6 Study Procedures**

The following procedures will be performed at the times shown in the Study Treatments  
Investigational Medical Products

- Test Product: DigiVibe Vibrating Anesthetic Device
- Non-Intervention: Standard of Care

### **4.6.1.1 Packaging, Labeling, and Storage**

The DigiVibe, Normal Saline, and injection/lancing supplies will be obtained from commercial batches and stored in their original packaging without adjustments or modifications to the labeling. The investigational product (DigiVibe) will not be masked.

Study Schedule of Activities (SOA):

#### Demography

Demography will be recorded at Visit 1 and will consists of date of birth, sex, ethnicity, and race.

#### Targeted Concomitant Medications

Targeted concomitant medications will be reviewed and recorded at Visit 1. A targeted concomitant medication is any NSAID, antiplatelet, anticoagulant, or analgesic treatment that the subject received within one (1) month of screening and enrollment into the study. All targeted concomitant medications should be documented in the subject's source documents.

#### Targeted Medical History

Targeted medical history will be reviewed and recorded at Visit 1. Targeted medical history includes medical events associated with the use of NSAIDs, antiplatelets, anticoagulants, and analgesics.

Vital Signs (height, weight, & blood pressure)

Subjects will have their height, weight, and blood pressure obtained using calibrated, digital devices. Vital signs will be documented in the subject's source documents.

Fingersticks and Injections (Without Intervention/DigiVibe)

Subjects will first undergo a fingerstick with a 30-gauge Unistik lancing device on their middle finger with no intervention (as per standard of care). For the fingerstick, the targeted area of the middle finger will be disinfected with alcohol, the lancing device will be pressed firmly against the pulp of the middle finger, and the lancet will be activated.

Subjects will then undergo a SC injection with a 30-gauge 4mm needle on the lower quadrant of their abdomen at least 2 inches from the belly button with no intervention (as per standard of care). For the SC injection, 0.5 mL of NS will be drawn into the syringe, the needle will be replaced with a new 30-gauge 4mm needle, the targeted area of the lower abdomen will be disinfected with alcohol, the needle will be inserted at a 90-degree angle, the NS will be injected slowly but steadily, and the needle will be withdrawn quickly.

Subjects will then undergo an IM injection with either a 25-gauge 1 inch needle or a 30-gauge 1 inch needle in upper arm deltoid muscle with no intervention (as per standard of care). For the IM injection, 0.5 mL of NS will be drawn into the syringe, the needle will be replaced with a new 25-gauge 1 inch needle or 30-gauge 1 inch needle (depending on the subject's assignment (see above)), the targeted area of the upper arm deltoid muscle will be disinfected with alcohol, the needle will be inserted at a 90-degree angle, the NS will be injected slowly but steadily, and the needle will be withdrawn quickly.

Fingersticks and Injections (With DigiVibe)

Subjects will undergo a fingerstick with a 30-gauge Unistik lancing device on their middle finger using the DigiVibe device. For the fingerstick, the targeted area of the middle finger will be disinfected with alcohol, the DigiVibe device will be applied to the pulp of the middle finger for 20 seconds, the lancet device will be inserted into the center of the DigiVibe device, and then the second fingerstick will be immediately performed with the DigiVibe device still vibrating through the release of the lancing device.

Subjects will then undergo a SC injection with a 30-gauge 4mm needle on the lower quadrant of their abdomen at least 2 inches from the belly button using DigiVibe device. For the SC injection, 0.5 mL of NS will be drawn into the syringe, the needle will be replaced with a new 30-gauge 4mm needle, the targeted area of the lower abdomen will be disinfected with alcohol, the DigiVibe device will be applied to the abdomen on the lower quadrant for 20 seconds, the needle will be inserted at a 90-degree angle through the center of the DigiVibe device (with the DigiVibe device still vibrating), the NS will be injected slowly but steadily, and the needle will be withdrawn quickly. The DigiVibe device should continue vibrating on the injection site during the entire injection process until the needle is removed.

Subjects will then undergo an IM injection with either a 25-gauge or 30-gauge 1 inch needle (depending on their previous assignment) in the upper arm deltoid muscle using the DigiVibe device. For the IM injection, 0.5 mL of NS will be drawn into the syringe, the needle will be replaced with a new 25-gauge or 30-gauge (depending on their assignment) 1 inch needle, the targeted area of the upper arm deltoid muscle will be disinfected with alcohol, the DigiVibe device will be applied to the deltoid muscle for 20 seconds, the needle will be inserted at a 90-degree angle through the center of the DigiVibe device (with the DigiVibe device still vibrating), the NS will be injected slowly but steadily, and the needle will be withdrawn quickly. The DigiVibe device should continue vibrating on the injection site during the entire injection process until the needle is removed.

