#### Visit 1 (Day1); In-Person Onsite Visit)

Subjects will be consented and assessed for eligibility to enroll in the study. Subject targeted concomitant medications and targeted medical history will be reviewed and recorded. The subjects BMI and vital signs will be obtained.

Following confirmation of eligibility, subjects will be enrolled. Subjects will first undergo two fingersticks with a 30-gauge Unistik lancing device on pulp of their middle finger. The first fingerstick will be performed with no intervention (as per standard of care).

Immediately following the fingerstick, subjects will be provided the VAS pain scale and asked to assess their level and pain and document it by circling the level of pain. After waiting 5 minutes, the DigiVibe device will be applied to the pulp of the other middle finger for 20 seconds, the lancet device will be inserted into the center of the DigiVibe device, and then the second fingerstick will be immediately performed with the DigiVibe device still vibrating through the release of the lancing device. Immediately following the fingerstick, subjects will be provided the VAS pain scale and asked to assess their level and pain and document it by circling the level of pain.

Subjects will then undergo two SC injections with a 30-gauge 4mm needle on the lower quadrant of their abdomen at least 2 inches from the belly button. The first SC injection will be performed with no intervention (as per standard of care). Immediately following the injection, subjects will be provided with the VAS pain scale and asked to assess their level and pain and document it by circling the level of pain. After waiting 5 minutes, the DigiVibe device will be applied to the other side of the abdomen on the lower quadrant for 20 seconds and then the second SC injection will be immediately performed with the DigiVibe device still vibrating the injection site during the entire injection process. Immediately following the SC injection, subjects will be provided the VAS pain scale and asked to assess their level and pain and document it by circling the level of pain.

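### The time from alcohol disinfection to puncture is not matched between conditions: none is prescribed for control, while a 20-second device application intervenes with DigiVibe at all three sites

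*Combined protocol and SAP*

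**What the plan says.** Section 4.6 describes each procedure twice, once without and once with the device.

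**Without DigiVibe.**
- Fingerstick: the site is "disinfected with alcohol, the lancing device will be pressed firmly against the pulp of the middle finger, and the lancet will be activated".
- SC: "the targeted area of the lower abdomen will be disinfected with alcohol, the needle will be inserted at a 90-degree angle".
- IM: the "deltoid muscle will be disinfected with alcohol, the needle will be inserted at a 90-degree angle".

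No wait or drying step is listed at any site.

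**With DigiVibe.**
- Fingerstick: the site is "disinfected with alcohol, the DigiVibe device will be applied to the pulp of the middle finger for 20 seconds", and the lancing device is then placed in the centre of the DigiVibe and fired.
- SC: the site is "disinfected with alcohol, the DigiVibe device will be applied to the abdomen on the lower quadrant for 20 seconds", then the needle goes in.
- IM: the site is "disinfected with alcohol, the DigiVibe device will be applied to the deltoid muscle for 20 seconds", then the needle goes in.

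Section 4.5 fixes the order of conditions, with control first at every site; for the finger, "The first fingerstick will be performed with no intervention (as per standard of care". It does not mention disinfection. Its 5-minute wait comes before the device is applied.

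Section 4.9.1 compares VAS scores under the two conditions by a paired t-test or Wilcoxon signed-rank test, separately for each site and with no other term.

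**The concern.** Section 4.1 attributes the expected benefit to vibration. The time elapsed since the skin was wiped with alcohol is not vibration, yet it follows condition completely: whichever stick is the DigiVibe stick also has the added 20 seconds. If that time has any influence on reported pain, the influence goes into the paired difference and is read as a device effect.

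No later analysis can remove it. The interval does not vary independently of condition, and nothing in the plan asks for it to be recorded. Randomising the order of conditions would not help either, because the interval would still follow condition. It can only be dealt with in the procedure, before data are collected.

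**Working it through.** **1. Step order, side by side (Section 4.6)**

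| Site | Control: between alcohol and puncture | DigiVibe: between alcohol and puncture |
|---|---|---|
| Finger | lancing device pressed on the skin; no time stated | 20 s application, then lancing device inserted |
| Abdomen (SC) | nothing listed | 20 s application |
| Deltoid (IM) | nothing listed | 20 s application |

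So the interval is at least 20 seconds with DigiVibe and unspecified for control, at three sites out of three. The 5-minute wait in Section 4.5 does not equalise it, because it falls before the device is applied and not between alcohol and puncture.

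**2. The plan's own figures**

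Inputs from Section 4.9.2 are n = 20, two-sided α = 0.05 and a paired t-test, with a difference of 1.0 at SD 1.5, or 0.75 at SD 1.0. Power comes from the noncentral t distribution with df = 19 and ncp = (difference/SD) × √20, where √20 = 4.472.

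- 1.0/1.5 × 4.472 = 2.98, giving power 80.7% (stated as at least 80%).
- 0.75/1.0 × 4.472 = 3.35, giving power 88.9% (stated as at least 88%).

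Both reproduce, and this point leaves them unchanged.

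**3. What an unmatched interval could do (illustration)**

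Set the true device effect to zero and let the interval add b points to the control score. Both the direction and the values of b (0.10, 0.25, 0.50, or 10%, 25% and 50% of the planned 1.0) are assumptions; the documents supply neither. Then ncp = (b/SD) × √20. The chance of a significant result favouring DigiVibe is P(T > 2.093), where T is noncentral t with df = 19 and 2.093 is the two-sided 5% critical value.

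| b | SD | ncp | Significant, favouring DigiVibe | Significant, either direction |
|---|---|---|---|---|
| 0 | either | 0 | 2.5% | 5.0% |
| 0.10 | 1.5 | 0.30 | 4.7% | 5.9% |
| 0.25 | 1.5 | 0.75 | 10.5% | 10.9% |
| 0.50 | 1.5 | 1.49 | 29.3% | 29.4% |
| 0.10 | 1.0 | 0.45 | 6.2% | 7.1% |
| 0.25 | 1.0 | 1.12 | 18.5% | 18.6% |
| 0.50 | 1.0 | 2.24 | 56.5% | 56.5% |

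The column that matters for a superiority claim is the one favouring DigiVibe, and its reference value is 2.5%, not 5%. At b = 0.25 the rate is 10.5/2.5 = 4.2 times the reference at SD 1.5, and 18.5/2.5 = 7.4 times at SD 1.0. Any shift of that size, from any cause, would give the same figures. They show how sensitive the test is and are not evidence about alcohol.

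**The case against.** **The control text does not say there is no pause.** It lists steps in order, gives no time, and refers to standard of care. Where the plan wants no delay it says so, as in the DigiVibe fingerstick. A reader might infer that the control puncture is made directly onto wet skin; the documents do not support that. What stands is narrower: no control interval is prescribed, timed or recorded, so equality could not be shown afterwards.

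**No mechanism is documented.** Nothing in the plan says that time since disinfection alters VAS scores, and the list of injection-site effects in Section 1.2 does not mention alcohol. A reader might infer that the trial is biased towards DigiVibe. That is not supported, since neither direction nor size is given. What stands is that the difference follows condition and cannot be separated from it.

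**The 20 seconds belongs to the device.** Section 4.2 compares DigiVibe with no intervention, and for the device as used, a stick without a wait is a legitimate comparator. This is partly a choice of what to estimate. But Section 4.1 attributes the benefit to vibration, and control can be given the same interval without any change to device use.

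**Equal time may not mean equal skin.** The device covers the site during its 20 seconds, whereas a control site would be uncovered, so drying may still differ. This stands as a limit of the fix.

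**Larger problems remain.** The fixed control-first order and the lack of blinding would still confound the comparison. That makes this point secondary, but solving those problems would not solve this one.

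**Conclusion.** The point holds as a possible, secondary bias. As written, Section 4.6 leaves the disinfection-to-puncture time unmatched at all three sites. With the steps done as listed, that time is longer with DigiVibe in every pair, and the planned paired test cannot distinguish its effect from that of vibration.

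The size is unknown. The range in the table (4.7% to 56.5% favouring DigiVibe, against 2.5%) rests on an assumed shift of 0.10 to 0.50 points against control, no true device effect, no other bias, and the SDs of 1.5 and 1.0 in Section 4.9.2. It should not be quoted as the trial's false-positive rate. The stated sample size and power are unaffected.

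The two fingerstick descriptions also differ on lancet contact: firm pressing appears only under control, while with DigiVibe the lancing device goes into the centre of the device. This is a minor wording point at one site. The documents do not show that the same pressure instruction could be followed through the device.

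**What to change.** In Sections 4.5 and 4.6, require the same interval from alcohol disinfection to puncture in both conditions at each site, and have it timed and recorded on the data collection form. The sponsor should choose the length; none is proposed here. Reconcile the lancet-contact wording in the two fingerstick descriptions as far as the device allows.

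The cost is a few lines of protocol text and about one extra minute per subject: three control procedures at roughly 20 seconds each, if the interval is close to the device application time. The control step becomes slightly more standardised than everyday practice. Matching time may not make skin drying fully equal, because the device covers the site. Device use, sample size and stated power do not change.

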#### Visual Analog Scale (VAS)

Subjects will be provided with a paper copy of the VAS, a validated scale that allows subjects to measure their pain on a visual horizontal grading scale of zero (0) to ten (10).

Subjects will use the VAS to provide their subjective measure of their pain level immediately following each fingerstick and injection for a total of six (6) completed scales.

#### Review AEs

AEs will be collected during the visit, which includes any new clinically significant sign or symptom or any clinically significant worsening of a pre-existing sign or symptom. The definitions of AEs and serious AEs (SAEs) are provided below.

#### Study Exit

After the procedures in the visit are complete, the subject is exited from the study.

### **4.7 Study Treatments**

#### **4.7.1 Investigational Medical Products**

- Test Product: DigiVibe Vibrating Anesthetic Device
- Non-Intervention: Standard of Care

##### **4.7.1.1 Packaging, Labeling, and Storage**

The DigiVibe, Normal Saline, and injection/lancing supplies will be obtained from commercial batches and stored in their original packaging without adjustments or modifications to the labeling. The investigational product (DigiVibe) will not be masked.

### **4.8 Study Schedule of Activities (SOA)**

Procedure	Screening/ Enrollment
	Visit 1/ Day 1
Informed Consent	X
Inclusion/Exclusion criteria	X
Demographics	X
Vital Signs (height, weight, & BP)	X
Targeted Medical History	X

Targeted Concomitant Medications	X
Fingerstick without DigiVibe	X
Subject VAS Pain Scale (post fingerstick without DigiVibe)	X
Subcutaneous Injection without DigiVibe	X
Subject VAS Pain Scale (post subcutaneous injection without DigiVibe)	X
Intramuscular Injection without DigiVibe	X
Subject VAS Pain Scale (post intramuscular injection without DigiVibe)	X
Fingerstick with DigiVibe	X
Subject VAS Pain Scale (post fingerstick with DigiVibe)	X
Subcutaneous Injection with DigiVibe	X
Subject VAS Pain Scale (post subcutaneous injection with DigiVibe)	X
Intramuscular Injection with DigiVibe	X
Subject VAS Pain Scale (post intramuscular injection with DigiVibe)	X
Adverse events	X
Study Exit	X
Data Entry	X

## 4.9 Data Analysis

### 4.9.1 Statistical Analysis Plan

Demographics and baseline characteristics of study subjects will be summarized, as will VAS pain scores for the intervention (DigiVibe) and standard care. The primary analysis will be a paired t-test or Wilcoxon signed-rank test (depending on normality of VAS scores) to compare pain scores between standard care and DigiVibe. These tests will be performed individually for each of the injection sites (fingerstick, SC, IM).

#### **4.9.2 Statistical Power and Sample Size Considerations**

For any of the three (3) injection sites individually, a sample size of 20 patients achieves  $\geq 80\%$  power to detect a mean of paired differences of 1.0 with an estimated standard deviation of differences of 1.5 and with a significance level ( $\alpha$ ) of 0.05 using a two-sided paired t-test. A smaller difference (e.g., 0.75) would be detectable with power  $\geq 88\%$  at an  $\alpha=0.05$  using the same test, if the standard deviation is 1.0.

### **4.10 Data Management**

#### **4.10.1 Data Collection and Storage**

Data required by the protocol will be collected using a data collection form created by the investigative site. The investigator has ultimate responsibility for the collection and reporting of all clinical data entered on the data collection form. Excel worksheets will be used to create the data repository for the analysis data set which will be de-identified and employ range checking derived from the study data dictionary. Final data merges for analysis will be performed with statistical analysis system (SAS) software. Electronic data will be stored on encrypted drives and backed up routinely to a secure server. At the End of Study completion, all electronic data will be stored on a password protected universal serial bus (USB) flash drive and archived with study documents.

Information about study subjects will be kept confidential and managed according to the requirements of the Health Insurance Portability and Accountability Act of 1996 (HIPAA). All physical records will be kept in a locked file cabinet.

#### **4.10.2 Records Retention**

The investigator must agree to archive the study documentation (both electronic and paper-based records) in an archive after completion or discontinuation of the trial. The investigator should not destroy any documents without prior permission from Suthe Dermal. If the investigator cannot archive the documents at the trial site, they should notify Suthe Dermal. At the conclusion of this study, data from this study will be archived for 2 years for possible use in future research studies.

## 5 SAFETY MONITORING

### 5.1 Adverse Event Reporting

Clinical AEs and SAEs will be monitored from signing of the ICF until completion of all study procedures are completed. All AEs and SAEs will be reported to an Investigator regardless of whether they are considered study-related. The date and time of onset and outcome, seriousness, intensity, action taken, and causality to study treatment will be assessed by a study investigator.

### 5.2 Definitions

An **adverse event** (AE) is any untoward, undesired, or unplanned event in the form of signs, symptoms, disease, or laboratory or physiological observations occurring in a person given a test article or in a clinical study. This includes a clinically significant worsening of a concomitant illness and clinical laboratory abnormalities which are clinically significant, i.e. an abnormality that suggests a disease and is of a severity that requires active management. The event does not need to be causally related to the device or clinical study.

The following definitions are used when assessing the intensity of an AE:

- Mild: no or transient symptoms, no interference with the subject's daily activities.
- Moderate: marked symptoms, moderate interference with the subject's daily activities.
- Severe: considerable interference with the subject's daily activities; unacceptable.

The following definitions are used when assessing the causality (relationship) of an AE:

- Related: A causal relationship between the study treatment and the AE is a reasonable possibility. The Investigator must further qualify the degree of certainty as "possible" or "probable."

- Possible: A causal relationship is conceivable and cannot be dismissed.
- Probable: Good reason and sufficient documentation to assume a causal relationship.
- Not Related: A causal relationship between the study treatment and the AE is not a reasonable possibility.

Items to be considered when assessing the relationship of an AE to the study treatment are:

- Temporal relationship of the onset of the event to the initiation of the study treatment;
- The course of the event, considering especially the effect of the discontinuation of study treatment or the reintroduction of study treatment, as applicable;
- Whether the event is known to be associated with the study treatment or with other similar treatments;
- The presence of risk factors in the study subject known to increase the occurrence of the event; and,
- The presence of non-study treatment-related factors that are known to be associated with the occurrence of the event.

The following definitions are used when assessing the outcome of an AE:

- Recovered/resolved: The subject has fully recovered, or by medical or surgical treatment the condition has returned to the level observed at the first trial-related activity after the subject signed the ICF.
- Recovering/resolving: The condition is improving, and the subject is expected to recover from the event. This term is only applicable if the subject has completed the trial or has died from another AE.
- Recovered/resolved with sequelae: The subject has recovered from the condition, but with lasting effect due to a disease, injury, treatment or procedure. If a sequela meets an SAE criterion, the AE must be reported as an SAE.
- Not recovered/not resolved: The condition of the subject has not improved, and

the symptoms are unchanged, or the outcome is not known.

- Unknown: This term is only applicable if the subject is lost to follow-up.

**SAEs** are any untoward medical occurrence affecting the pain site:

- Results in death;
- Is life-threatening (i.e., the subject was at immediate risk of death from the AE as it occurred; this does not include an event that, had it occurred in a more severe form or was allowed to continue, might have caused death);
- Requires inpatient hospitalization or prolongation of existing hospitalization;
- Results in persistent or significant disability/incapacity;
- Is a congenital anomaly/birth defect;
- Is a medically important event.

